#### **2.4.1 Exploratory end points:**

- a. Expansion/persistence and in vivo effects of infused T cells assessed by a range of T cell measures
- b. Endogenous immune reconstitution/antibody induction
- c. Extended safety of T cell infusion to day 28 and 42 post-infusion
- d. Incidence of Mechanical Ventilation [ Time Frame: Up to 60 days ]
- e. Incidence of advanced ventilation (proning, oscillator or extracorporeal membrane oxygenation or use of inhaled pulmonary vasodilators) [ Time Frame: Up to 60 days ]
- f. Ventilator-Free Days to Day 28 [ Time Frame: Up to Day 28 ]
- g. Organ Failure-Free Days to Day 28 [ Time Frame: Up to Day 28 ]
- h. Incidence of Intensive Care Unit (ICU) Stay [ Time Frame: Up to 60 days ]
- i. Duration of ICU Stay [ Time Frame: Up to 60 days ]
- j. Time to Clinical Failure [ Time Frame: From time of infusion to time of death, mechanical ventilation, ICU admission, or study withdrawal (whichever occurs first, for up to 60 days) ]
- k. Overall Mortality [ Time Frame: Up to 60 days ]
- l. Time to COVID-related Mortality [ Time Frame: Up to 60 days ]
- m. Time to Hospital Discharge [ Time Frame: Up to 60 days ]
- n. Incidence and duration of Supplemental Oxygen [ Time Frame: Up to 60 days ]
- o. Time to Reverse-Transcriptase Polymerase Chain Reaction (RT-PCR) Virus Negativity [ Time Frame: Up to 60 days ]
- p. Serum Concentration of biomarkers of T cell activation

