#### **2.8. Risks and Mitigation strategies for Toxicities in the Treatment Arm.**

### **2.8.1. Graft Versus Host Disease (GVHD).**

The risk that adoptively transferred partially HLA-matched VSTs will cause Grade II or higher GVHD is low in these patients, the majority of whom will be partially or fully immunocompetent. According to data from previous studies [15, 16] even allogeneic transplant recipients whose immune function is substantially impaired had a low frequency of significant GVHD after treatment with 3rd party VSTs specific for adenovirus, EBV, CMV, BK and HHV6 ([Section 1.6](#)). If any subject develops GVHD they will receive our standard GVHD treatment as per [SOP F08.03](#). GVHD will be monitored for 2 weeks following infusion. Weekly GVHD organ stage scores (up to 2 weeks post infusion), overall clinical grade, biopsy information for GVHD and relevant differential diagnosis will be recorded. The weekly score will encompass all information since the last assessment. Organ involvement, biopsy information, staging, differential diagnosis, and GVHD therapy will be documented in the medical record using the Blood and Marrow Transplant Clinical Trials Network (BMT CTN) GVHD scoring stamp or equivalent.

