#### **3.2. Antiviral Activity.**

We will assess the efficacy of SARS-CoV2 specific T cells by comparing the proportion of patients in the treatment arm with those in the control arm (only during the randomized phase of the study) who have a clinical response by day 7 post-randomization (measured as an improvement in their WHO ordinal scale score by 2 or more points or if the patients gets discharged from hospital). When available radiographic response information will also be compared between both groups as well as several other exploratory end-points as listed in section 2.3.

The schedule of monitoring for safety and antiviral activity is demonstrated below.

Table 1. REQUIRED ASSESSMENTS					
	Day-5 to Day -1 (pre-infusion)	Day 0	Days 1-14 (daily)	Days 15 to resolution of treatment-related toxicity (if applicable)	Month 2, 3 and 6
Consent, COVID testing and HLA-typing (research test)	X				
T cell infusion (dose escalation phase) or Randomization  (randomized phase) (research)		X			
History		X	X**	X	X
Acute GVHD and CRS/ICANS evaluation (research) §		X §	X*	X*	
Chemistries: Liver function tests (alkaline phosphatase, bilirubin, AST, ALT), ferritin, DDimer, LDH and CRP §		X	X*/**	X*	
Pregnancy test (research) 	X				
Infusion related toxicity evaluation (research) §		X	X*/**	X*	
Clinical response assessment (WHO ordinal scale)		X	X**	X*	
Chest imaging	X (within 48 hrs of randomization)		X** (at least once post infusion)		
Blood and serum for ancillary laboratory studies (research) 		X	X*/**	X*	X***
CBC with Differential		X	X*/**	X*	X***
Basic Chemistry		X	X*/**	X*	X***

\*At a minimum weekly assessments needed until resolution of all treatment-related toxicities

\*\*Until discharge from hospital

\*\*\*2, 3 and 6 month labs optional and billed to research if performed; history may be obtained via telephone if necessary, off study will be assessed per criteria in [Section 4.3.2](#).

§: Not required for patients randomized to the standard of care arm (control arm)

1: Pregnancy test where applicable (research test)

2: Research procedures beyond that required for usual care - 30-40mls or 6-8 teaspoons may be collected at each time point. Depending on clinical and laboratory responses samples may be collected at additional time points

3: T cells must be infused within 48 hours of randomization.

Research laboratory studies may include:

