#### Post-Treatment/Randomization.

1. Daily Clinical improvement as measured by the ordinal scale (until day 14)
2. Daily history, collect blood and serum for ancillary lab studies, and CBC with differential (until day 14 or until discharge from hospital whichever comes first, refer to Table 1 for more details)
3. Chest-imaging (at least once post infusion by day 14)
4. Case Report Form (CRF) to include:
  - a. Complete acute GVHD staging and grading information (including skin, liver, upper and lower GI) assessed at a minimum weekly for the first 2 weeks and longer until resolution of GVHD if it develops (only for treatment arm).
  - b. Chemistries: liver function tests (bilirubin, alkaline phosphatase, AST, ALT), ferritin, DDimer, LDH and CRP, done at least weekly while hospitalized. If discharged no further chemistry testing is necessary.
  - c. Infusion-related toxicities assessed at a minimum weekly for the first 2 weeks and longer until resolution of any treatment related adverse events. (only treatment arm). This must include at least weekly assessment of immune effector related toxicities like CRS/ICANS per ASTCT grading.

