#### **4.6. Data Analysis**

All patients who received VSTs infusions or standard of care will be included in the safety analyses. All patients infused with SARS-CoVSTs and finish their 14-day toxicity observation or develop a DLT/tAE before day 14 are considered DLT/tAE evaluable. All efficacy analysis will be based on the intent to treat (ITT) population, defined as eligible and randomized subjects.

Adverse events and corresponding toxicity grades after study treatment will be summarized descriptively by phases then arms. Toxicity information including the type, severity, time of onset, time of resolution, and the probable association with study treatments will be tabulated and summarized. Incidence of DLT/tAE in patients who receive VST infusions defined in [Section 3.1 and 3.4.1](#), will be reported with rates and 95% binomial exact confidence intervals.

Clinical responses will be summarized using rates and 95% binomial exact confidence intervals for the randomized pilot trial phase by arms and compared using Fisher's exact test. Anti-COVID19 efficacy assessed by the WHO ordinal scale will be evaluated every day up to day 14 post-randomization. The assessments will be summarized using descriptive statistics such as medians and ranges. Plots of the assessments over time will be generated for each patient to graphically illustrate the pattern and trend of clinical status. The changes in scales by day 14 post randomization will also be computed; percentages of patients with stable ordinal scale, with worse or improved scales will be summarized by arms.

Clinical exploratory end points (requirement of supplemental oxygen, progression to mechanical or advanced ventilation or ICU, mortality rate, duration on oxygen supplementation, duration of ventilation free, duration of organ failure-free, durations of ICU stay and hospital stay, time to RT-PCR virus negativity) will be summarized in a descriptive nature by arms. Categorical variables will be summarized by frequencies and percentages, and continuous variables will be summarized by means, standard deviations, medians, interquartile ranges. Clinical endpoints will be compared between arms using Fisher's exact tests or Wilcoxon rank sum tests, whichever is appropriate. All statistical tests for clinical exploratory endpoints will be considered exploratory

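### The assessment schedule does not fully support three exploratory or descriptive analyses: WHO change by day 14, safety to days 28 and 42, and time to PCR negativity

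*Protocol*

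**What the plan says.** **WHO score.** Section 4.6 states: "Anti-COVID19 efficacy assessed by the WHO ordinal scale will be evaluated every day up to day 14 post-randomization". It then adds "The changes in scales by day 14 post randomization will also be computed", with the percentages stable, worse and improved given by arm. Section 3.3 agrees: "Daily Clinical improvement as measured by the ordinal scale (until day 14" and no limit at discharge. In Section 3.3 the discharge limit belongs to the next item (history, research samples and blood count). Table 1 in Section 3.2 differs. Its row "Clinical response assessment (WHO ordinal scale" carries a double asterisk for days 1-14, and that footnote reads "Until discharge from hospital".

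**Extended safety.** Exploratory endpoint 2.4.1(c) is "Extended safety of T cell infusion to day 28 and 42 post-infusion". Section 2.8.1 says "GVHD will be monitored for 2 weeks following infusion". Section 5.2.1 collects adverse events for 14 days after dosing, except that infusion-related toxicities are followed to resolution. Section 5.2.2 collects serious adverse events for 3 months. Table 1 has a column after day 14 that applies only while a treatment-related toxicity is unresolved, and then months 2, 3 and 6.

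**PCR.** Exploratory endpoint 2.4.1(o) is "Time to Reverse-Transcriptase Polymerase Chain Reaction (RT-PCR) Virus Negativity", up to 60 days. Section 4.6 lists it among the clinical endpoints summarised by arm and compared by Fisher's exact or Wilcoxon tests. Table 1 schedules COVID testing only in the five days before infusion or randomization.

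**The concern.** An analysis plan can define how missing values are handled, but it cannot recover observations that the schedule never asked for. In each of the three cases a planned summary needs data that the schedule, read literally, does not collect.

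For the WHO score, the reason for missingness is the outcome itself. Patients who go home stop being scored, and more are expected to go home on the VST arm. Medians and ranges computed from recorded scores alone would describe the patients still in hospital.

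For safety, a statement about days 28 and 42 would rest on serious events and on toxicities already being followed, with no active search for new milder ones.

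For PCR, a time-to-event comparison would rest on swabs taken at clinicians' choice. The control arm receives no placebo (Section 2.7), so those clinicians can know the treatment.

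**Working it through.** **Inputs.** Section 4.5 gives 20 patients per arm and expected day-7 response of 90% (VST) and 50% (control). It states 83% power for Fisher's exact test at one-sided 5%. Exact enumeration over all 21 × 21 outcomes gives 83.7%, so these are the planning rates in use. Nothing in this point changes that figure.

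**WHO score: how many patients would lose it.** Let f be the share of day-7 responses that are discharges. The protocol does not give f; 0.5 to 1 is assumed.

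- Discharged by day 7, VST: 20 × 0.90 × f = 18f, which is 9 to 18.
- Discharged by day 7, control: 20 × 0.50 × f = 10f, which is 5 to 10.
- Both arms: 28f, which is 14 to 28 of 40, or 35% to 70%.
- Still scored under Table 1 after day 7, before any later discharges: 20 − 18f = 2 to 11 on VST and 20 − 10f = 10 to 15 on control.

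The upper part of this range is plausible. In Appendix III every hospitalized state scores 3 or more, so a patient who starts at 3 or 4 can gain two points only by leaving hospital. Only a patient at 5 or above could respond as an inpatient. Entry requires oxygen saturation of at least 92% on room air (Section 2.6.1), which points to low starting scores, but the protocol gives no baseline distribution.

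**WHO score: what can be recovered.** A patient alive and out of hospital scores 0, 1 or 2; any inpatient scores at least 3. Discharge therefore implies improvement unless the patient is readmitted or dies before day 14. What cannot be recovered is the exact score, and hence the medians, ranges and individual plots promised in Section 4.6, and any readmission that nobody asked about. Appendix III also records each day the worst score of the previous day, so the last recorded score before discharge is an inpatient one and should not be carried forward.

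**Safety: what is covered between day 14 and day 42.**

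- Serious adverse events: yes, to 3 months (5.2.2).
- Treatment-related toxicities under follow-up, including GVHD that has developed: yes, to resolution (5.2.1, 3.3).
- History at months 2, 3 and 6: yes (Table 1, 3.3), but neither day 28 nor day 42 is a contact, and the GVHD and toxicity rows are blank at those months.
- New non-serious adverse events, and low-grade GVHD starting after day 14: not systematically sought.

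**PCR.** After the baseline test, no PCR appears in Table 1, in the Section 3.3 lists or among the research laboratory studies. Section 3.3 only permits additional assessments prompted by clinical and laboratory responses. The date of first negativity therefore depends on whether and when someone chose to swab.

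**The case against.** The strongest reply is that these are three exploratory or descriptive items and the main endpoints are sound. That stands. Discharge counts as response at day 7, so the primary endpoint needs no score after discharge, and the secondary safety endpoint ends at day 14, inside the collection window. Section 4.6 labels the tests on clinical exploratory endpoints as exploratory.

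It can also be said that Table 1 is a single inconsistent footnote, and that the handling of scores after discharge may be left to an analysis plan that is not shown. This stands in part. The protocol contradicts itself rather than uniformly stopping the score, and a rule could assign a direction of change. No rule can supply readmissions or exact scores that were not collected.

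A reader might infer three stronger conclusions that the documents do not support.

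- *That a patient who enters at 3 and goes home can never be counted as improved, or that the day-14 table must be computed on the sickest patients.* Appendix III makes the improvement inferable, and no section prescribes a complete-case analysis; efficacy is on the intent-to-treat population.
- *That extended safety will look clean by construction.* Serious events and related toxicities are captured at days 28 and 42. Nor does the earlier banked-VST study in Section 1.6, which reports GVHD within 45 days, show that the same risk applies here. Its patients were allogeneic transplant recipients, and 6 of the 8 with GVHD had a prior history of it. Section 1.6 expects lower risk outside transplantation and cell persistence of about 2 weeks.
- *That 28 of 40 scores will be missing.* That is the upper limit at f = 1, and it requires Table 1 to override Sections 3.3 and 4.6.

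On PCR the only reply is that the endpoint is one of 16 exploratory ones. That limits its weight but does not remove the gap.

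**Conclusion.** The concern holds as a mismatch between the schedule and three exploratory or descriptive analyses. It is moderate in weight, and no sample size, power or stopping figure changes.

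- **WHO change by day 14:** an internal contradiction. If Table 1 is followed, outcome-dependent loss of scores affects about 9-18 of 20 VST and 5-10 of 20 control patients. This rests on the 90% and 50% planning rates and the assumed 50-100% discharge share. Because direction is mostly inferable, it would be too strong to say that the analysis cannot be done.
- **Extended safety:** partly supported. The gap is new non-serious events and low-grade GVHD with onset after day 14.
- **Time to PCR negativity:** the between-arm comparison is not supported by any scheduled test after baseline.

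**What to change.** 1. **WHO score.** Remove the discharge limit from the WHO row of Table 1 so that it matches Sections 3.3 and 4.6. In both arms, obtain status after discharge by telephone at least at day 14: home, readmitted or dead, and whether activities are limited. Assign patients alive and out of hospital a score of 2 or less. A call cannot establish score 0, which requires absence of virological evidence of infection, so the rule should say how 0 is treated.
2. **Extended safety.** Either restrict 2.4.1(c) to serious adverse events and treatment-related toxicities already being followed, which needs no new data, or add telephone symptom contacts at days 28 and 42 for infused patients and extend 5.2.1 to match. MAGIC staging (Appendix II) needs bilirubin, rash extent and stool output, so a call can screen but not grade. Suspected GVHD would have to be referred for in-person assessment.
3. **PCR.** Remove the between-arm comparison from Section 4.6 and report available clinical PCR results descriptively, or delete 2.4.1(o). Keep the comparison only if fixed swab days are already used in both arms.

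The cost is wording in Table 1, 2.4.1, 4.6 and possibly 5.2.1, plus a few calls per patient. Section 3.3 already allows teleconference for the late history visits, but this would extend it to new purposes. Deleting 2.4.1(o) would remove the only endpoint that names viral clearance; descriptive reporting keeps that information without an unsupported comparison.

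### Hospital stay, ICU stay and time to PCR negativity are assigned a rank-sum test, with no value set for patients who die or never reach the event

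*Protocol*

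**What the plan says.** Section 4.6 (Data Analysis) names "durations of ICU stay and hospital stay, time to RT-PCR virus negativity" among the clinical exploratory endpoints. It says that "continuous variables will be summarized by means, standard deviations, medians, interquartile ranges", and that arms are compared with Fisher's exact tests or "Wilcoxon rank sum tests, whichever is appropriate". For a duration or a time, the rank-sum is the one of the two that applies. The section adds that "All statistical tests for clinical exploratory endpoints will be considered exploratory".

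Section 2.4.1 lists the same endpoints as "Time to Hospital Discharge [ Time Frame: Up to 60 days", "Duration of ICU Stay [ Time Frame: Up to 60 days" and "Time to Reverse-Transcriptase Polymerase Chain Reaction (RT-PCR) Virus Negativity [ Time Frame: Up to 60 days" (each time frame in brackets). Two of the three are therefore times to an event within a fixed window.

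Only time to clinical failure gets a method for censored data (Kaplan-Meier and log-rank, end of section 4.6). The only explicit rule for scoring a death in an efficacy endpoint is in section 4.5, where death before day 7 counts as non-response for the primary endpoint. Section 4.6 bases all efficacy analysis on the intent-to-treat population, so patients who die belong in these comparisons.

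**The concern.** A rank-sum test needs one number per patient, ordered so that lower is better or worse for everyone. Length of stay has that property only among patients who leave hospital alive. A patient who dies in hospital on day 3 has a recorded stay of 3 days, and a patient who dies on the ward has 0 ICU days, tied with the best survivors. If those values enter as recorded, an arm with more early deaths gains good ranks from them. A patient still in hospital at day 60 has no discharge time at all.

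PCR negativity has a different problem. A patient who dies while positive, stays positive or is never re-tested has no time to rank.

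At stake is how far the stay and viral-clearance results of this pilot can be read between arms, for example when planning a later trial.

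**Working it through.** The plan states no figure for these endpoints, so there is none to reproduce. The check asks how a rank-sum on raw hospital stay behaves when mortality differs between arms.

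**Inputs.** From section 4.5: 20 patients per arm. Assumed, because the protocol gives no such figures: mortality 5% in one arm and 20% in the other; the same stay distribution for survivors in both arms (log-normal, median 6 days, log-SD 0.7); death times log-normal with log-SD 0.5 and a median varied from day 4 to day 14.

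**Formula.** Let θ be the probability that a death time is shorter than a survivor's stay, and let p_H and p_L be the higher and lower mortality. If survivors' stays are alike in the two arms, the probability that a patient in the higher-mortality arm has the shorter stay is

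P = 0.5 + (p_H − p_L)(θ − 0.5).

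For log-normal times, θ = Φ[ln(median stay / median death time) / √(0.7² + 0.5²)], with √0.74 = 0.860. Ranking death worst sets θ = 0.

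The standard deviation of the rank-sum estimate of P, with no difference and 20 per arm, is √[41/(12 × 400)] = 0.0924. The share of trials leaning toward the higher-mortality arm is therefore about Φ[(P − 0.5)/0.0924].

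**Results, mortality 5% versus 20% (difference 0.15).**

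| Median death day | θ | P | Share leaning to the higher-mortality arm |
|---|---|---|---|
| 4 | 0.681 | 0.527 | 62% |
| 6 | 0.500 | 0.500 | 50% |
| 8 | 0.369 | 0.480 | 42% |
| 10 | 0.276 | 0.466 | 36% |
| 14 | 0.162 | 0.449 | 29% |
| any, death ranked worst | 0 | 0.425 | 21% |

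Simulations on the same inputs agree: 60% to 62% at day 4, 49% to 51% at day 6, 36% at day 10, and about 79% leaning to the lower-mortality arm when death is ranked worst. Even at day 4, only about 5% of trials reach p < 0.05 in the wrong direction, against about 2.5% with no difference.

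**Sensitivity to mortality.** With 5% versus 10% and deaths at median day 4, P = 0.5 + 0.05 × 0.181 = 0.509, against 0.475 with death ranked worst, so the effect is small. With a median stay of 8 days (log-SD 0.6) and deaths at median day 4, simulated P is 0.53 for 15% versus 5% and 0.56 for 30% versus 10%. With death ranked worst it is 0.45 and 0.40. With equal mortality (10% in each arm) both scorings give 0.50.

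The formula shows what drives the sign. The raw comparison points the wrong way only when deaths tend to come before the typical discharge (θ > 0.5). When they come later, it points the right way but is weaker than it should be.

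**PCR negativity.** No arithmetic applies. Table 1 (section 3.2) lists COVID testing only in the pre-infusion column, and the post-treatment list in section 3.3 contains no PCR. Section 3.3 allows additional assessments according to clinical and laboratory responses, and section 2.7 states that controls receive no placebo. Any re-testing may therefore depend on clinical course and on known treatment, and a rank-sum among those re-tested compares selected subsets.

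**The case against.** The strongest reply is that section 4.6 is silent on death and states no rule to ignore it. Worst-rank scoring fits within a Wilcoxon test, and a statistical analysis plan, not shown here, could specify it. This stands as far as it goes: a reader might infer that the protocol tells the analyst to count an early death as a good outcome, and the text does not say that. It does fix the test and the summaries, however. It offers only two tests for endpoints that it elsewhere calls times to an event, and means and standard deviations of stay have no place for a worst rank or a censored time.

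A reader might also infer that the comparison will generally reverse. It need not. Reversal requires deaths before the typical discharge, and the protocol does not support that timing: eligible patients saturate at 92% or more on room air (section 2.6.1) and are neither ventilated nor on vasopressors (section 2.6.2), so later deaths are at least plausible. Constructed datasets can look more alarming. Replacing the four longest of 20 control stays by deaths on days 2 to 5 gives p = 0.07 in favour of the arm with the deaths, but replacing four middle or evenly spread stays gives p = 0.35. The smaller value comes from choosing who dies.

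Two further extensions are not supported. An early death does not score as a favourable time to PCR negativity, because it has no value. No fault has been shown here for ventilator-free or organ-failure-free days.

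Finally, the tests are declared exploratory, mortality is reported as its own endpoint, and death is an event in time to clinical failure. All of this stands and limits the severity.

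**Conclusion.** The point holds as a minor one. Section 4.6 assigns uncensored summaries and a rank-sum test to endpoints for which death and non-attainment are possible, and gives such patients no value. If stays are taken as recorded, the hospital-stay comparison is biased toward the higher-mortality arm when deaths are early and diluted when they are late. With mortality of 5% versus 20% and a median stay of 6 days, the lean toward the higher-mortality arm is about 60%, 50% and 36% for deaths at median day 4, 6 and 10, against about 21% with death ranked worst. These sizes rest on assumed mortality, stay and timing, and they shrink with a smaller mortality difference. ICU stay shares the mechanism through ward deaths scored as 0 days; its size was not computed. For PCR negativity the fault is unobserved and selectively observed times. No primary, secondary or stopping decision uses these comparisons.

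**What to change.** In section 4.6:

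- **Hospital stay.** Analyse time to discharge from randomisation to day 60 by cumulative incidence, with death as a competing event (for example Gray's test). Alternatively, keep the rank-sum and give the worst ranks to death and to non-discharge by day 60.
- **ICU stay.** Give death the worst rank in the between-arm comparison, and show deaths separately beside the descriptive summary.
- **PCR negativity.** Report it descriptively among patients actually re-tested, with the number re-tested in each arm, and make no between-arm test.

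The cost is a few sentences in the protocol or analysis plan and a little more analysis. No new data are needed.

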### **2.6.3. Informed Consent and Randomization.**

The informed consent process will begin at recognition of a subject who meets all eligibility criteria and consents to participation after a discussion with the study team (informed consent process). Consent may be obtained by teleconference. Once enrolled, blood will be taken from the subject for baseline immune response assessment and HLA-typing and if a partially HLA-matched VST line is available the subject will either receive treatment (dose escalation phase) or will be randomized (Randomized trial phase) to receive the partially matched VST line (in the treatment arm) or standard of care (in the control arm). If no VST line is identified, the patient will not proceed to treatment or randomization and will be removed from the study, but statistics on the proportion of patients who sign consent but are not treated or randomized will be reported.

Applicable only to the randomized phase, once randomized to the treatment arm, the patient must be infused with VSTs within 48 hours of randomization.

All consented patients will be registered in the online collaborative research environment (Forte's OnCore® eResearch CTMS), a Clinical Research Management System available at BCM Dan L. Duncan Comprehensive Cancer Center.

Enrollment to the dose escalation phase will be staggered. The first patient enrolled on each of the 3 dose levels (DL1, DL2 and DL3) will have to complete the 14-day toxicity monitoring window prior to enrollment of the next patients. Prior to dose escalation, all patients at a particular dose level should have completed the minimum 14-day toxicity monitoring window before enrolling to a higher dose level.

After the dose finding phase, patients will be randomized in a 1:1 ratio to receive SARS-CoVSTs at the MTD level or standard of care. Randomization will be performed in OnCore and use the permuted block method with a block size of 4 (2 in the treatment arm and 2 in the control arm). The purpose for a permuted block method is to ensure fairly random assignment during specific periods of surge with COVID19.

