#### **2.7. Standard of care arm (only for the randomized phase of this study).**

Patients randomized to the standard of care arm will continue to receive treatments for COVID19 as determined by institutional protocols. They will not receive a placebo.

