Time to clinical failure is defined as the days from VST infusion to date of death, mechanical ventilation, ICU admission, or study withdrawal, whichever occurs first. Patients without those clinical failure events up to 14 days will be considered censored. Time to clinical failure will be estimated in each arm by the Kaplan-Meier method and compared using log-rank tests.

Laboratory data, which include expansion and persistence of infused VSTs, inflammatory markers, biomarkers of T cell activation, will be summarized with appropriate summary statistics. Changes from pre- to post-infusion will be plotted for each patient who receives the VST infusion over time and assessed using paired comparisons when appropriate.

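### Time to clinical failure, an exploratory endpoint, starts at VST infusion, so its between-arm log-rank comparison cannot be computed as written, and its horizon is 14 days in one section and 60 in another

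*Protocol*

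**What the plan says.** Section 4.6 of the protocol sets the origin and the events: "Time to clinical failure is defined as the days from VST infusion to date of death, mechanical ventilation, ICU admission, or study withdrawal". Items 2.4.1(j) and 2.4.2(g) use the same origin and the same four events.

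Section 4.6 then makes it a between-arm analysis: "Time to clinical failure will be estimated in each arm by the Kaplan-Meier method and compared using log-rank tests". Its horizon is given as "Patients without those clinical failure events up to 14 days will be considered censored", whereas the two endpoint lists have "whichever occurs first, for up to 60 days".

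Other provisions bear on this:

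- Section 2.7, on control patients: "They will not receive a placebo".
- Section 2.6.3, on the VST arm: "once randomized to the treatment arm, the patient must be infused with VSTs within 48 hours of randomization".
- Section 4.6 bases every efficacy analysis on eligible, randomized subjects (intention to treat).
- Section 3.3 times the randomized-phase assessments from randomization, and the primary response endpoint in Section 2.2.1 is also counted from randomization.
- Section 4.6 labels the tests of clinical exploratory endpoints as exploratory.

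**The concern.** A log-rank test needs a day 0 that exists in both arms and means the same thing in each. Infusion exists in one arm only. Even there it comes after randomization, and a patient who deteriorates first may never reach it: exclusion criterion 2 rules out anyone on mechanical ventilation when the T cells are to be given.

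As the text stands, someone must later choose a control-arm origin and one of two horizons, in an unblinded trial with 20 patients per arm, where one or two patients can change the picture. Counting study withdrawal as failure adds a further sensitivity, because patients know their allocation when they decide whether to stay.

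**Working it through.** **1. The plan's own efficacy figure.** Section 4.5 states 83% power for day-7 response: 90% against 50%, 20 per arm, Fisher's exact test, one-sided 5%. Power = Σ over (a, b) of Bin(a; 20, 0.9) × Bin(b; 20, 0.5) × 1[Fisher p ≤ 0.05] = 83.7%, so the figure is reproduced. It concerns a different endpoint with a randomization clock. No event count, hazard ratio or power is stated for time to clinical failure.

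**2. Can the endpoint be computed?** Let R be randomization, L the lag to infusion (0 to 2 days) and E the event time. The defined time is E − (R + L).

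- Control arm: there is no infusion, so the time is undefined for 20 of 40 patients.
- VST arm, event before infusion: the time is negative.
- VST arm, never infused: the time is undefined.

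The intention-to-treat set includes all of these patients, so the rule and the population conflict.

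**3. What the obvious fallback would do.** Suppose controls start at R and VST patients at R + L, and VST patients who fail before infusion drop out. The protocol gives no failure rates, so these are assumptions: 14-day failure F of 20% or 40% in both arms (no true effect), and S(t) = exp(−λt^k) with λ = −ln(1 − F)/14^k. Shape k = 1 is constant hazard and k = 0.6 is front-loaded. L is uniform on 0-2 days, with 20 per arm, a 14-day horizon and 4,000 replicates. Rejection is one-sided in favour of VST, nominal 5%.

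| F | k | Both from randomization: HR, rejection | Mixed origin: HR, rejection | Mean VST patients lost (of 20) |
|---|---|---|---|---|
| 20% | 1.0 | 1.00, 4.6% | 0.99, 5.6% | 20 − 19.68 = 0.32 |
| 20% | 0.6 | 1.00, 4.6% | 0.82, 8.2% | 20 − 19.14 = 0.86 |
| 40% | 1.0 | 0.98, 5.3% | 0.99, 5.6% | 20 − 19.28 = 0.72 |
| 40% | 0.6 | 1.00, 4.7% | 0.84, 8.8% | 20 − 18.11 = 1.89 |

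With constant hazard, the risk after infusion equals the risk after randomization, so dropping the lag leaves the hazard ratio near 1, though patients still leave the intention-to-treat set. With front-loaded hazard, the VST clock skips the period of highest risk.

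**4. Withdrawal counted as failure.** Both arms start at randomization, with F = 20% and k = 1. Withdrawal is independent of failure, and the 14-day withdrawal rates are assumed.

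| Withdrawal, VST vs control | Counted as failure: HR, rejection | Censored: HR, rejection |
|---|---|---|
| 0% vs 10% | 0.67, 15.0% | 1.01, 5.0% |
| 0% vs 20% | 0.50, 30.6% | 1.00, 5.0% |
| 10% vs 10% | 1.01, 4.8% | 1.01, 4.6% |

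The distortion needs withdrawal that differs by arm.

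**5. 14 days against 60.** With assumed 60-day failure F60, the share of events by day 14 is [1 − (1 − F60)^((14/60)^k)] / F60. For F60 = 20% and k = 1 this is (1 − 0.8^0.2333)/0.20 = 0.0507/0.20 = 25%.

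| F60 | k = 1 | k = 0.6 | k = 0.4 |
|---|---|---|---|
| 20% | 25% | 44% | 59% |
| 40% | 28% | 48% | 62% |

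A 14-day cut would thus discard 38% to 75% of the 60-day events under these assumptions. It applies equally to both arms, and with a common origin the null hazard ratio at 14 days is 0.98-1.00 (step 3).

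**The case against.** The strongest reply is that this is item (j) in a list of 16 exploratory endpoints, and that no bias has been demonstrated. Much of that stands. A reader might infer that the log-rank test is biased towards VST, that VST patients gain up to two event-free days, or that this is the trial's main comparison of clinical deterioration. The documents support none of these.

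- The comparison is undefined rather than shown to be biased; the mixed origin in step 3 is a fallback that the protocol never states.
- With an infusion clock, the days before infusion are left out, not credited as follow-up. The harm, if any, comes from losing early failures.
- That harm needs front-loaded failures. Eligibility requires SpO2 of at least 92% on room air and excludes ventilated patients and those on vasopressors, so heavy failure in the first two days is not established.
- Withdrawal counts as failure in both arms, consistently in all three places, and no withdrawal rates are given. Censoring withdrawals is no clear improvement either, since it misleads if withdrawal is related to prognosis.
- The horizon mismatch loses events but does not favour an arm.

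What the reply does not remove is the express text: an origin that one arm lacks, and two horizons that cannot both apply. A statistical analysis plan may exist, but the protocol's wording would still be wrong.

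**Conclusion.** The point holds as a definitional error in one exploratory endpoint. As written, time to clinical failure has no day 0 for the control arm or for uninfused VST-arm patients, which contradicts the intention-to-treat rule and the randomization clock used elsewhere. Section 4.6 also contradicts Sections 2.4.1 and 2.4.2 on the horizon.

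Bias is conditional. Under the mixed-origin fallback with front-loaded failures (assumed Weibull shape 0.6, 14-day failure 20-40%, uniform lag), the null hazard ratio is about 0.82-0.84 and one-sided rejection about 8-9% instead of 5%. Under constant hazard it is not material. Counting withdrawal as failure distorts the result only if withdrawal differs by arm, which is plausible without a placebo but not shown.

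The primary endpoint and its 83% power are unaffected. This is a correction to make before any between-arm analysis, not a threat to the trial's main conclusion.

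**What to change.** In Sections 2.4.1(j), 2.4.2(g) and 4.6:

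1. For the randomized phase, start time to clinical failure at randomization in both arms. Keep infusion as the origin only in the dose-finding phase.
2. State one horizon in all three places. It can be day 60, as the endpoint lists have it, once capture of ICU and ventilation dates to that day is confirmed, or day 14.
3. Keep withdrawal as a failure event if the sponsor wishes, and add a sensitivity analysis that censors withdrawals at the withdrawal date.

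The cost is a wording change and one extra sensitivity analysis. Day 60 may also need extra date capture: daily ordinal scores stop at day 14, later follow-up is by history at months 2, 3 and 6, the ordinal scale has no ICU category, and the data list in Section 5.1 does not itemise ICU or ventilation dates.
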